9.1.1 Imaging Assessment for the Study

At the Sponsor's discretion, de-identified scans and measurements may be collected and reviewed by independent radiologists using RECIST 1.1 criteria at a later date, or at any time during the study.

9.2 Adverse Events

The definitions of an AE or serious adverse event (SAE) can be found in [Appendix 3](#).

AEs will be reported by the participant (or, when appropriate, by a caregiver, surrogate, or the participant's legally authorized representative).

The investigator and any designees are responsible for detecting, documenting, and reporting events that meet the definition of an AE or SAE and remain responsible for following up AEs that are serious, considered related to the study treatment or the study, or that caused the participant to discontinue before completing the study.

Contacts for SAE reporting specified in Appendix 3

Immune-mediated adverse events are AEs consistent with an immune-mediated mechanism or immune-mediated component for which non-inflammatory etiologies (eg, infection or tumor progression) have been ruled out. IMAEs can include events with an alternate etiology which were exacerbated by the induction of autoimmunity. Information supporting the assessment will be collected on the participant's case report form.

9.2.1 Time Period and Frequency for Collecting AE and SAE Information

The collection of non-serious AE information should begin at initiation of study treatment until 100 days after the last dose of study therapy, at the timepoints specified in the Schedule of Activities ([Section 2](#)). Non-serious AE information should also be collected from the start of a placebo lead-in period or other observational period intended to establish a baseline status for the participants.

Sections 5.6.1 and 5.6.2 in the Investigator Brochure (IB) represent the Reference Safety Information to determine expectedness of SAEs for expedited reporting. Following the participant's written consent to participate in the study, all SAEs, whether related or not related to study drug, must be collected, including those thought to be associated with protocol-specified procedures.

All SAEs must be collected that occur during the screening period and within 100 days after discontinuation of dosing. If applicable, SAEs must be collected that relate to any later protocol-specified procedure (eg, a follow-up skin biopsy).

The investigator must report any SAE that occurs after these time periods and that is believed to be related to study drug or protocol-specified procedure.

- Medical occurrences that begin before the start of study treatment but after obtaining informed consent will be recorded on the appropriate section of the eCRF section.
- All SAEs will be recorded and reported to Sponsor or designee within 24 hours, as indicated in [Appendix 3](#).
- The investigator will submit any updated SAE data to the sponsor within 24 hours of this being available.

Investigators are not obligated to actively seek AEs or SAEs in former study participants. However, if the investigator learns of any SAE, including a death, at any time after a participant has been discharged from the study, and he/she considers the event reasonably related to the study treatment or study participation, the investigator must promptly notify the sponsor.

The method of evaluating, and assessing causality of AEs and SAEs and the procedures for completing and reporting/transmitting SAE reports are provided in [Appendix 3](#).

9.2.2 Method of Detecting AEs and SAEs

Adverse events can be spontaneously reported or elicited during open-ended questioning, examination, or evaluation of a participant. (In order to prevent reporting bias, participants should not be questioned regarding the specific occurrence of one or more AEs.)

9.2.3 Follow-up of AEs and SAEs

- Non-serious AEs should be followed to resolution or stabilization, or reported as SAEs if they become serious (see [Appendix 3](#)).
- Follow-up is also required for non-serious AEs that cause interruption or discontinuation of study treatment and for those present at the end of study treatment as appropriate.
- All identified non-serious AEs must be recorded and described on the non-serious AE page of the CRF (paper or electronic). Completion of supplemental CRFs may be requested for AEs and/or laboratory abnormalities that are reported/identified during the course of the study.

After the initial AE/SAE report, the investigator is required to proactively follow each participant at subsequent visits/contacts. All SAEs, and non-serious AEs of special interest (as defined in [Section 9.2](#)) will be followed until resolution, until the condition stabilizes, until the event is otherwise explained, or until the participant is lost to follow-up (as defined in [Section 8.3](#)).

Further information on follow-up procedures is given in [Appendix 3](#).

9.2.4 Regulatory Reporting Requirements for SAEs

- Prompt notification by the investigator to the Sponsor of SAEs is essential so that legal obligations and ethical responsibilities towards the safety of participants and the safety of a product under clinical investigation are met.
- An investigator who receives an investigator safety report describing SAEs or other specific safety information (eg, summary or listing of SAEs) from the Sponsor will file it along with the Investigator's Brochure and will notify the IRB/IEC, if appropriate according to local requirements.

Sponsor or designee will be reporting AEs to regulatory authorities and ethics committees according to local applicable laws including European Directive 2001/20/EC and FDA Code of Federal Regulations 21 CFR Parts 312 and 320. A SUSAR (Suspected, Unexpected Serious Adverse Reaction) is a subset of SAEs and will be reported to the appropriate regulatory authorities and investigators following local and global guidelines and requirements. All SAEs must be collected that occur during the screening period and within 100 days of the last dose of study treatment. For participants randomized/assigned to treatment and never treated with study drug, SAEs should be collected for 30 days from the date of treatment assignment.

9.2.5 Pregnancy

If, following initiation of the study treatment, it is subsequently discovered that a participant is pregnant or may have been pregnant at the time of study exposure, including during at least 5 half-lives after product administration, the investigator must immediately notify the BMS Medical Monitor/designee of this event and complete and forward a Pregnancy Surveillance Form to BMS Designee within 24 hours of awareness of the event and in accordance with SAE reporting procedures described in [Appendix 3](#).

In most cases, the study treatment will be permanently discontinued in an appropriate manner (eg, dose tapering if necessary for participant safety). Please call the BMS Medical Monitor within 24 hours of awareness of the pregnancy.

Follow-up information regarding the course of the pregnancy, including perinatal and neonatal outcome and, where applicable, offspring information must be reported on the Pregnancy Surveillance Form.

Any pregnancy that occurs in a female partner of a male study participant should be reported to Sponsor or designee. In order for Sponsor or designee to collect any pregnancy surveillance information from the female partner, the female partner must sign an informed consent form for disclosure of this information. Information on this pregnancy will be collected on the Pregnancy Surveillance Form.

9.2.6 Laboratory Test Result Abnormalities

The following laboratory test result abnormalities should be captured on the non-serious AE CRF page or SAE Report Form electronic, as appropriate. Paper forms are only intended as a back-up option when the electronic system is not functioning.

- Any laboratory test result that is clinically significant or meets the definition of an SAE
- Any laboratory test result abnormality that required the participant to have study treatment discontinued or interrupted
- Any laboratory test result abnormality that required the participant to receive specific corrective therapy

It is expected that wherever possible, the clinical rather than laboratory term would be used by the reporting investigator (eg, anemia versus low hemoglobin value).

9.2.7 Potential Drug Induced Liver Injury (DILI)

Wherever possible, timely confirmation of initial liver-related laboratory abnormalities should occur prior to the reporting of a potential DILI event. All occurrences of potential DILIs, meeting the defined criteria, must be reported as SAEs (see [Section 9.2](#) and [Appendix 3](#) for reporting details).

Potential drug induced liver injury is defined as:

- 1) AT (ALT or AST) elevation > 3 times upper limit of normal (ULN), **AND**;
- 2) Total bilirubin > 2 times ULN, without initial findings of cholestasis (elevated serum alkaline phosphatase), **AND**;
- 3) No other immediately apparent possible causes of aminotransaminase (AT) elevation and hyperbilirubinemia, including, but not limited to, viral hepatitis, pre-existing chronic or acute liver disease, or the administration of other drug(s) known to be hepatotoxic.

9.2.8 Other Safety Considerations

Any significant worsening noted during interim or final physical examinations, electrocardiogram, x-ray filming, any other potential safety assessment required or not required by protocol should also be recorded as a non-serious or SAE, as appropriate, and reported accordingly.

9.3 Overdose

An overdose is defined as the accidental or intentional administration of any dose of a product that is considered both excessive and medically important. All occurrences of overdose must be reported as an SAE (see [Section 9.2](#)).

In the event of an overdose the investigator/treating physician should:

- 1) Contact the Medical Monitor immediately
- 2) Closely monitor the participant for AEs/SAEs and laboratory abnormalities
- 3) Document the quantity of the excess dose as well as the duration of the overdosing in the CRF.

Decisions regarding dose interruptions or modifications will be made by the investigator in consultation with the Medical Monitor based on the clinical evaluation of the participant.

9.4 Safety

Planned time points for all safety assessments are listed in the Schedule of Activities. Safety assessments include AEs, physical examinations, vital signs, ECOG performance status, assessment of signs and symptoms, laboratory tests, and pregnancy tests as outlined in the Schedule of Activities.

9.4.1 Electrocardiograms

Refer to Schedule of Activities. A 12-lead ECG must be performed during the screening phase, preferably after eligibility has been confirmed. This will serve as a baseline assessment in the event of any on-study cardiac AEs. Vital signs should also be taken as per institutional standard of care prior to, during and after infusions.

9.4.2 Clinical Safety Laboratory Assessments

- Investigators must document their review of each laboratory safety report.
- All clinical safety laboratory assessments will be performed locally per the Schedule of Activities and Table 9.4.2-1.

| Table 9.4.2-1: Laboratory Assessment Panels | |
|---|---|
| Hematology | |
| Hemoglobin | |
| Hematocrit | |
| Total leukocyte count, including differential | |
| Platelet count | |
| Serum Chemistry | |
| Aspartate aminotransferase (AST) | Sodium |
| Alanine aminotransferase (ALT) | Potassium |
| Total bilirubin | Chloride |
| Alkaline phosphatase | Calcium |
| Creatinine | Phosphate |
| Blood Urea Nitrogen (BUN) or Serum Urea Level | Lipase |
| Glucose | Amylase |
| Uric acid | TSH (reflex to free T3 and T4 if abnormal) |
| | Creatinine clearance (CrCL) calculation using Cockcroft-Gault at screening only and every 6 weeks for participants with renal impairment. |
| Serology | |
| Serum for hepatitis C antibody or hepatitis C RNA, hepatitis B surface antigen (screening only) | |
| When mandated locally, HIV testing must be performed. HIV testing is required for all participants in Germany | |

| |
|---|
| Table 9.4.2-1: Laboratory Assessment Panels |
| (see Appendix 9). |
| Other Analyses |
| Pregnancy test and FSH (WOCBP only, as described in Section 2). |

9.4.3 Imaging Safety Assessment

Not Applicable.

9.5 Pharmacokinetic Assessment

Samples for PK and immunogenicity assessments will be collected for all participants receiving nivolumab and ipilimumab as described in Table 9.5.1-1. All time points are relative to the start of study drug administration. All on-treatment time points are intended to align with days on which study drug is administered, if dosing occurs on a different day, the PK and immunogenicity sampling should be adjusted accordingly. Further details of sample collection, processing, and shipment will be provided in the laboratory procedures manual.

9.5.1 Pharmacokinetic and Immunogenicity Collection and Processing: All Cohorts

A detailed schedule of PK and immunogenicity evaluations is provided in Table 9.5.1-1. PK samples will be analyzed for nivolumab/ipilimumab by a validated ligand binding assay. Immunogenicity samples will be analyzed for anti-nivolumab antibodies/anti-ipilimumab antibodies by a validated immunogenicity assay; samples may also be analyzed for neutralizing antibodies by a validated method. Serum samples may be analyzed by an exploratory method that measures anti-drug antibodies for technology exploration purposes; exploratory results will not be reported. Serum samples designated for PK or biomarker assessments may also be used for immunogenicity analysis if required (eg, insufficient volume for complete immunogenicity assessment or to follow up on suspected immunogenicity related AE).

| Table 9.5.1-1: Pharmacokinetic and Immunogenicity Sample Collection for Nivolumab and Ipilimumab (All Cohorts) | | | | | | |
|---|--|--|--|---|---|--|
| Study Day^a (1 Cycle = 6 weeks) | Event (Relative To Dosing) Hour | Time (Relative To Dosing) Hour: Min | PK Blood Sample for Nivolumab | IMG Blood Sample for Nivolumab | PK Blood Sample for Ipilimumab | IMG Blood Sample for Ipilimumab |
| C1D1 (Nivolumab + Ipilimumab dose 1) | Predose ^b | 00:00 | X | X | X | X |
| C1D1 | 0.5 (EOI) ^c | 00:30 ^c | X | | X | |
| C1D15 ^d (Nivolumab dose 2) | Predose ^b | 00:00 | X | X | X | X |

| Table 9.5.1-1: Pharmacokinetic and Immunogenicity Sample Collection for Nivolumab and Ipilimumab (All Cohorts) | | | | | | |
|--|--|--|--|---|---|--|
| Study Day^a (1 Cycle = 6 weeks) | Event (Relative To Dosing) Hour | Time (Relative To Dosing) Hour: Min | PK Blood Sample for Nivolumab | IMG Blood Sample for Nivolumab | PK Blood Sample for Ipilimumab | IMG Blood Sample for Ipilimumab |
| C2D15 ^d (Nivolumab dose 5) | Predose ^b | 00:00 | X | X | X | X |
| C4D15 ^d (Nivolumab dose 11) | Predose ^b | 00:00 | X | X | X | X |
| D15 of every 4th cycle after C4D15 until discontinuation of study treatment or maximum up to 2 years of treatment ^d | Predose ^b | 00:00 | X | X | X | X |

^a If ipilimumab is discontinued and nivolumab continues, ipilimumab PK and ADA should be collected only for the next 2 time points (corresponding to nivolumab sample collection) according to the PK table.

^b Predose samples should be collected just before the administration of the first drug (preferably within 30 minutes). If it is known that a dose is going to be delayed, then the predose sample should be collected just prior to the delayed dose. However, if a predose sample is collected but the dose is subsequently delayed, an additional predose sample should not be collected.

^c EOI: End of Infusion. This sample should be taken immediately prior to stopping the second drug infusion (preferably within 2 minutes prior to the end of infusion). If the end of infusion is delayed to beyond the nominal infusion duration, the collection of this sample should also be delayed accordingly. EOI samples may not be collected from the same IV access as drug was administered.

^d If the D15 PK collection is missed, PK can be collected at next visit, D29.

9.6 Pharmacodynamics

Pharmacodynamic parameters are not evaluated in this study.

9.7 Pharmacogenomics

Pharmacogenomic testing will not be performed in this study.

9.8 Biomarkers

9.8.1 Tumor Tissue Specimens

9.8.1.1 Cohorts A, A1, and B

[figure not shown]
Fresh or archival FFPE tumor tissue collected within 12 months (block) or within 6 months for sectioned slides) must be submitted for PD-L1 IHC testing prior to the treatment assignment for all cohorts. Previously generated PD-L1 results are also acceptable if generated using anti-PD-L1 antibodies 28-8, 22-C3 or SP263. If results using approved antibodies are provided, then additional PD-L1 testing is not required. PD-L1 results generated using the SP142 antibody are not acceptable. If PD-L1 status is unknown then samples will be sent to a third party to stain and

[figure not shown]
score for PD-L1 expression using the PD-L1 IHC 28-8 pharmDx kit (Dako). Stained tissue samples will be assessed by a pathologist at a central lab identified by the Sponsor and scored as PD-L1 expressing if membrane staining is observed in $\geq 1\%$ tumor cells among a minimum of 100 evaluable tumor cells.

[figure not shown]

9.8.1.2 Cohort C

Archival FFPE tumor tissue collected within 3 months or fresh tissue for sectioned slides must be submitted for TMB testing. Ten unstained tumor tissue sections are required for TMB testing by Foundation Medicine unless TMB previous results from Foundation Medicine are available. PD-L1 testing is required unless results available from another BMS study, or a commercially available complementary diagnostic using an acceptable antibody (ie, 28-8, 22-C3, SP263). PD-L1 results obtained using antibody SP142 are not acceptable. Cohort C tissue will be assessed for biomarkers, as other cohorts.

9.9 Healthcare Resource Utilization and Health Economics

Health Economics/Medical Resource Utilization and Health Economics parameters will not be evaluated in this study.

9.10 Patient Reported Outcomes

[figure not shown]
In this study, patient-reported outcomes (PRO) will be measured using the Functional Assessment of Cancer Therapy-Lung (FACT-L) Version 4, a quality of life questionnaire to assess various functional dimensions and includes the Lung Cancer Subscale (LCS) that specifically assesses the treatment impact on lung cancer-related symptoms. The FACT-L is provided in [Appendix 8](#).

10 STATISTICAL CONSIDERATIONS

10.1 Sample Size Determination

In this study, approximately 400 participants will be treated in Cohort A and 400 participants will be treated in Cohort B.

In general, for nivolumab combined with ipilimumab, the safety profile to date is similar across tumor types, while select treatment related AEs of high grade (Grade 3-4) are rather uncommon. Their incidence per category was $\leq 5\%$ in the CA209012 trial that tested nivolumab 3 mg/kg every 2 weeks and ipilimumab 1 mg/kg every 6 weeks.¹³

An additional special population NSCLC cohort (Cohort A1) will include approximately 200 treated participants with one or more of the following criteria: ECOG PS 2, or PS ≤ 1

asymptomatic untreated brain metastases, renal or hepatic dysfunction, and/or HIV. Descriptive safety and efficacy analysis based on this cohort (Cohort A1) will be performed. [REDACTED]

[REDACTED]

Approximately 300 participants will be screened for TMB to achieve approximately 100 treated participants in Cohort C. [REDACTED]

[REDACTED]

[REDACTED]

10.2 Populations for Analyses

| Population | Description |
|--|---|
| Enrolled | All participants who signed informed consent and were registered in IVRS |
| Treated | All participants who take at least 1 dose of any study medication. |
| Primary NSCLC cohorts treated participants | All treated participants in Cohort A and B. This is the primary cohort for safety and efficacy analyses |
| Special population NSCLC | All treated participants in the special population cohort (A1). |

| Population | Description |
|-----------------------------|--|
| cohort treated participants | Exploratory analysis will be conducted by special populations. |
| PK | All treated participants with available serum time-concentration data. |
| Immunogenicity | All treated participants with available immunogenicity data. |

10.3 Statistical Analyses

10.3.1 Efficacy Analyses

The primary efficacy analysis is scheduled to occur once all patients have initiated study therapy and have been followed for at least 9 months.

| Endpoint | Statistical Analysis Methods |
|----------------------------------|--|
| Secondary in Cohorts A, B, and C | 
Objective Response Rate (ORR) defined as the number and percentage of participants with a best overall response (BOR) of confirmed complete response (CR) or partial response (PR). Best overall response (BOR) is defined as the best response designation, recorded between the date of first dose and the date of the initial objectively documented tumor progression per RECIST v1.1 or the date of subsequent therapy, whichever occurs first. For participants without documented progression or subsequent therapy, all available response designations will contribute to the BOR determination.
 
The ORR will be summarized by binomial response rates and their corresponding two-sided 95% exact CIs using the Clopper-Pearson method.
 |
| Secondary in Cohorts A, B and C | 
Progression-free survival (PFS) is defined as the time from first dosing date to the date of the first documented tumor progression, as determined by investigators (per RECIST v1.1), or death due to any cause, whichever occurs first. Participants who die without a reported prior progression will be considered to have progressed on the date of their death. Participants who did not progress or die will be censored on the date of their last evaluable tumor assessment. Participants who did not have any on study tumor assessments and did not die will be censored on the first dosing date. Participants who started any palliative local therapy or subsequent anti-cancer therapy without a prior reported progression will be censored on the date of their last evaluable tumor assessment prior to the initiation of the palliative local therapy or subsequent anti-cancer therapy, whichever procedure occurred first.
 
OS is defined as the time from first dosing date to the date of death. A participant who has not died will be censored at last known date alive.
 
OS and PFS will be summarized by Kaplan-Meier (KM) product-limit method for all treated participants. Median values of OS and PFS, along with two-sided 95% CI using Brookmeyer and Crowley method, will be calculated. Survival
 |

| Endpoint | Statistical Analysis Methods |
|-------------|---|
| | 
rates at fixed timepoints (eg, at 6 months) will also be estimated using KM estimates on the OS curve for all treated participants. Associated two-sided 95% CIs will be calculated using the Greenwood formula.
 
Duration of objective response (DOR) is defined as the time between the date of first confirmed response to the date of the first documented tumor progression (per RECIST 1.1), or death due to any cause, whichever occurs first. Participants who neither progress nor die will be censored on the date of their last evaluable tumor assessment. Participants who started any subsequent anti-cancer therapy without a prior reported progression will be censored at the last evaluable tumor assessment prior to or on the date of initiation of the subsequent anti-cancer therapy. DOR will be evaluated for responders (ie, participants with confirmed CR or PR) only.
 |
| Exploratory | Will be described in the statistical analysis plan finalized before database lock |

10.3.2 Safety Analyses

The primary safety analysis is scheduled to occur once all patients have initiated study therapy and have been followed for at least 3 months.

| Endpoint | Statistical Analysis Methods |
|--------------------------------|--|
| Primary in Cohorts A, B, and C | 
The number and percentage of participants who experience high grade (Grade 3-4 and Grade 5) treatment related select and immune-mediated adverse events (imAEs) will be summarized for all treated participants. High grade (Grade 3-4 and Grade 5) treatment related select AEs and imAEs will be tabulated using worst grade per NCI CTCAE v4 criteria by system organ class and Medical Dictionary for Regulatory Affairs (MedDRA) preferred term. The analysis is scheduled to occur once all patients have initiated study therapy and have been followed for at least 3 months.
 
The (select AEs consist of a list of preferred terms grouped by specific category (eg, pulmonary events, gastrointestinal events categories, etc). AEs that may differ from or be more severe than AEs caused by non-immunotherapies and AEs whose early recognition and management may mitigate severe toxicity are included as select AEs. The select AEs and the categories are defined by the Sponsor and the list that is the most current at the time of analysis will be used. Changes may be made to this list with each new version of MedDRA prior to database lock. Only select AEs occurring within 30 days of the last dose are included in the analysis.
 
Immune-mediated AEs are specific events (or groups of preferred terms [PTs] describing specific events) that include pneumonitis, diarrhea/colitis, hepatitis,
 |

| Endpoint | Statistical Analysis Methods |
|-------------|--|
| | nephritis/renal dysfunction, rash, and endocrine (adrenal insufficiency, hypothyroidism/thyroiditis, hyperthyroidism, diabetes mellitus, and hypophysitis). IMAE analyses included events, regardless of causality, occurring within 100 days of the last dose. These analyses will be limited to participants who received immunosuppressive medication for treatment of the event, with the exception of endocrine events (hypothyroidism/thyroiditis, hyperthyroidism, hypophysitis, diabetes mellitus, adrenal insufficiency), which were included in the analysis regardless of treatment since these events are often managed without immunosuppression. |
| Exploratory | Will be described in the statistical analysis plan finalized before database lock |

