| FACT-L | X | X | For participants who have discontinued study therapy, but continue to be followed for radiographic progression per Section 9.1.1, the FACT-L must be collected at each visit. On the day of study visits that include FACT-L assessment, the assessment will be performed PRIOR to any study procedures and treatment. FACT-L assessments may be administered in office or over the telephone. Section 9.10 |

Table 2-3: Follow-up and Survival Procedures (CA209817) - All participants

| Procedure | Follow-Up Visits 1 & 2 ^a | Survival Follow-up Visits ^b | Notes |
|---|-------------------------------------|--|---|
| Efficacy Assessments | | | |
| Radiographic Tumor Assessment (CT chest and known sites of disease. Repeat CT/MRI of abdomen with or without pelvis is required for participants with metastases in those areas at baseline, or if clinically indicated.) | X | X* | Section 9.1.1. For participants who discontinue study treatment for reasons other than progressive disease, follow up scans should be performed every 6 weeks (± 1 wk) up to Week 48, then every 12 weeks until progressive disease, initiation of subsequent systemic therapy, lost to follow-up, or withdrawal of consent. *Radiographic assessments for participants who have not experienced progressive disease must be obtained every 6 weeks (± 7 days), and not delayed until follow-up visits 1 & 2. |
| Collection of Survival Status and Subsequent Therapy Information | X | X | Collect every 3 months in Survival Visits until death, lost to follow-up, or withdrawal of study consent. May be performed by phone contact or office visit. Additional subsequent cancer therapy details such as regimen, setting of the regimen, line of therapy, start date and end date of each regimen, best response to the regimen and date of progression after second line therapy will be collected. |

^a Follow-Up Visit 1 to occur 35 days from the last dose (± 7 days) or coinciding with the date of discontinuation of study drug (± 7 days) if the date of discontinuation is greater than 42 days from the last dose. Follow-Up Visit 2 to occur 80 days from Follow-Up Visit 1 (± 7 days) . Patients should be monitored continuously (at least up to 100 days after the last dose) as an adverse reaction with nivolumab or nivolumab in combination with ipilimumab may occur at any time during or after discontinuation of therapy.

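### Treatment-related high-grade non-endocrine select AEs that start 31 to 100 days after the last dose and receive no immunosuppression are collected but counted in neither part of the primary safety endpoint

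*Combined protocol and SAP*

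**What the plan says.** The synopsis and Table 4-1 define the primary endpoint as the number and percentage of participants with high-grade (Grade 3-4 and Grade 5) treatment-related select AEs and imAEs, separately for Cohorts A, B and C. Neither place gives a time window.

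Section 10.3.2 supplies the windows. For select AEs: "Only select AEs occurring within 30 days of the last dose are included in the analysis". For imAEs: "IMAE analyses included events, regardless of causality, occurring within 100 days of the last dose". A further condition applies to imAEs: "These analyses will be limited to participants who received immunosuppressive medication for treatment of the event, with the exception of endocrine events". The primary safety analysis takes place "once all patients have initiated study therapy and have been followed for at least 3 months". Exploratory safety analyses are deferred to the statistical analysis plan.

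Data collection runs longer than the select-AE window. Section 9.2.1 collects non-serious AEs "until 100 days after the last dose of study therapy", and section 9.2.4 collects SAEs "within 100 days of the last dose of study treatment". Footnote a of Table 2-3 asks for monitoring to at least day 100, on the ground that reactions can arise after treatment has stopped. In the same footnote: "Follow-Up Visit 1 to occur 35 days from the last dose", with a tolerance of 7 days either way. That is nominally after the select-AE window has closed.

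**The concern.** The purpose of the trial is to characterise high-grade immune toxicity of the combination. One part of its primary endpoint closes 70 days before data collection does, and the visible text gives no reason. The other part stays open to day 100 but admits non-endocrine events only if they were treated with immunosuppression. An event can therefore be severe, judged related to treatment and recorded on the case report form, yet appear in neither primary table. A hypothetical case is a treatment-related fatal pneumonitis that begins on day 40, where death comes before any steroid is given.

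A second point affects how the same tables are read. Section 10.3.2 is unclear about whether an imAE must be treatment-related to count.

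**Working it through.** The plan gives no figure that depends on these windows, so there is nothing to reproduce. The check applies the counting rules to each kind of event and then gives the scale.

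**1. Inputs.** Select-AE window: 30 days after the last dose (10.3.2). imAE window: 100 days, with the immunosuppression condition and the endocrine exemption (10.3.2). Collection: 100 days (9.2.1, 9.2.4). Select categories: seven, including hypersensitivity/infusion reaction (Table 4-1). The imAE list in 10.3.2 does not name that category. Treated participants: about 400 in each of Cohorts A and B and about 100 in Cohort C (10.1).

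**2. Rules applied to a treatment-related Grade 3-5 select AE.**

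| Onset after last dose | Event | Immunosuppression | Collected | Select-AE part | imAE part |
|---|---|---|---|---|---|
| to day 30 | any select category | either | yes | yes | depends on type and treatment |
| days 31-100 | endocrine, on imAE list | either | yes | no | yes |
| days 31-100 | non-endocrine, on imAE list | given | yes | no | yes |
| days 31-100 | non-endocrine, on imAE list | not given | yes | no | **no** |
| days 31-100 | hypersensitivity/infusion reaction | either | yes | no | **no** |

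The last two rows are the gap. The last is largely theoretical, since onset so late is unlikely. Onset after day 100 is outside both parts under any window up to 100 days.

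**3. Length of the difference.** 100 - 30 = 70 post-dose days are collected but not used for select AEs.

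**4. Scale per participant.** 1/400 = 0.25 percentage points; 1/100 = 1.0 percentage point.

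**5. Illustration, on assumptions.** Sections 3.2.4 and 10.1 cite at most 5% per category in the earlier trial. Assume a full 100-day rate of 5% in 400 participants: 0.05 x 400 = 20 (5.0%, exact 95% CI 3.08 to 7.62). The share of these falling in the gap is unknown. If it were:
- 5%: 20 - 1 = 19 counted, 4.75%;
- 10%: 20 - 2 = 18 counted, 4.5%;
- 20%: 20 - 4 = 16 counted, 4.0%.

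Even the largest assumed share moves the estimate by 1.0 point, which is inside the interval.

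**6. Follow-up visits.** In the standard case Visit 1 falls on days 35 - 7 = 28 to 35 + 7 = 42. Visit 2 is 80 days later (±7): earliest 28 + 73 = 101, latest 42 + 87 = 129. No follow-up visit is scheduled on days 43-100, so onsets in that period are generally recorded in retrospect.

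**7. Maturity at the primary safety analysis.** 3 x 30.44 = about 91 days, which is less than 100. A participant with only 3 months of follow-up cannot have completed 100 post-dose days.

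**8. Causality of imAEs.** The opening of the primary row in 10.3.2, like the synopsis and Table 4-1, places treatment-related before both select AEs and imAEs and can be read as covering both. Later in the same row imAEs are counted whatever their cause (quoted above). The two readings count different participants.

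**The case against.** The strongest reply is that this is an openly stated design choice. Section 10.3.2 pairs two measures: attributed events over a short window, and immune-mediated events of any cause over a long one. No passage promises a 100-day select-AE rate, and any shorter window gives an equal or lower percentage. That stands. The 30-day rate is not an error, and its being lower is not in itself evidence of bias.

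A reader might infer that all late high-grade toxicity is lost. The document does not support this: the imAE part recovers late endocrine events and late listed events treated with immunosuppression. Appendix 8 describes corticosteroids as a primary therapy for such events, so most late high-grade events probably enter there.

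A reader might also infer that the uncounted events go unreported or unmonitored. That does not follow either. They are collected to day 100, and section 5.1.2 describes real-time review of SAEs and periodic review of all AE data. Exploratory safety analyses are deferred to an SAP that is not in the document and might include a 100-day select-AE table. What can be said is that the primary tables, as written, omit these events.

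Finally, at the 3-month analysis the 30-day window will be complete for more participants than the 100-day window, so a 100-day table would be less mature. This is a reason to keep the 30-day table and to report window completion. It does not remove the gap.

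**Conclusion.** The concern holds as a minor point. The gap follows directly from the counting rules. Its direction is known: extending the window can only leave the select-AE percentage unchanged or raise it. Its size cannot be derived from the document and is probably small. Section 3.1.1 states that there is no formal hypothesis, so no test, threshold or decision is affected. It is worth acting on because it concerns the primary endpoint of a safety trial and the data are already being collected.

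The conclusion assumes that the 30-day limit means onset up to 30 days after the last dose, with on-treatment events included, and that the imAE list in 10.3.2 is complete as printed. If the list is wider, the hypersensitivity/infusion row may shrink; the row for listed events without immunosuppression is unaffected.

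The conflict over imAE causality is a separate wording fault. It lies inside 10.3.2 as well as between that section and the synopsis and Table 4-1.

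**What to change.** In section 10.3.2:

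- Keep the 30-day select-AE table, which preserves comparability with other 30-day tables.
- Add a table of high-grade treatment-related select AEs with onset from first dose to 100 days after the last dose. Do not truncate it at subsequent anti-cancer therapy, because that would again leave some late events uncounted; alternatively, show events after the start of such therapy separately. Table 2-3 already collects regimen start dates.
- Label the select-AE and imAE parts separately, each with its window and causality rule.
- Choose one causality rule for imAEs and use it in the synopsis, in Table 4-1 and in both places in 10.3.2.
- At the primary safety analysis, state how many participants are still on treatment or have not completed 100 days after the last dose. Update the 100-day tables in later reporting, and name when. The visible text commits to no later safety update; the 9-month analysis in 10.3.1 is an efficacy analysis.

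The cost is some wording and one extra table set with its update. No new data collection is needed. The reported select-AE percentage may rise slightly.
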